### Methodology

A single center randomized control trial approach will be employed. Adult patients admitted post cardiac surgery with a sternotomy incision will be randomized into the intervention (n=75) or control group (n=75). Units will include the cardiac surgical intensive care unit, the coronary care unit and the cardiovascular telemetry unit. Intervention will include the use of a silver dressing on the sternotomy incisions and the donors sites where applicable. The control group will follow standard care processes. Data collection will include a checklist and the modified Parsonnet Score. Data analysis will include descriptive and inferential statistics.

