### Conclusion

The current rate of surgical site infection amongst cardiac surgical patients is 2.1 below the benchmark of 2.9 with an operational goal of 2.1.

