## **Research Setting and study population**

**King Faisal Specialist Hospital and Research Center- Jeddah**, a specialist referral and research center, which is a 390 bedded facility with three main domains of care namely Ambulatory Care (20 units), Nursing Speciality (13 departments), and Nursing General Services (10 departments). Patients admitted to Cardiac surgical intensive unit (CSICU), Coronary Care Unit (CCU) and Cardiovascular Telemetry- Adult (CVT Adult) Unit after cardiac surgery with a sternal wound.

In 2023 there was a total of 150 of adult cardiac patients admitted post cardiac surgery with a mediastinal incision.

[figure not shown]

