## Sampling technique

**Principal Investigator:**

**Name (print**      **Signature:** \_\_\_\_\_ **Date:** \_\_\_\_\_

The study will follow a randomised sampling approach. Randomisation will include: first patient transferred from OR to the CSICU will be part of the intervention group, second patient part of the control group. This sequence will be followed until the required sample size is reached.

Sample size will include:

In the year 2023 there were a total of 200 patients admitted for a cardiac surgical procedure requiring a mediastinal incision. Based on this population and sample size calculation- a total of 109 patients will be included – meeting the inclusion and exclusion criteria.

Ie 55 in the intervention group and 54 in the control group.

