### **Inclusion criteria**

- Patients 14 years of age and older scheduled for cardiac surgery requiring a sternotomy incision.

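### The protocol states two sample sizes, 150 and 109, with nothing to reconcile them, and rests 109 on an admission count that cannot by itself size a two-arm comparison of SSI rates

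*Protocol*

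**What the plan says.** **Sample size.** The abstract (section 4, Methodology) says that patients "will be randomized into the intervention (n=75) or control group (n=75"), which makes 150. Sampling technique, in the body of the proposal, says "Based on this population and sample size calculation- a total of 109 patients will be included" and adds "Ie 55 in the intervention group and 54 in the control group". That section also fixes when enrolment ends: patients alternate between the arms and "This sequence will be followed until the required sample size is reached".

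**Basis for 109.** Immediately before the 109, Sampling technique states: "In the year 2023 there were a total of 200 patients admitted for a cardiac surgical procedure requiring a mediastinal incision". It also names a sample size calculation but shows none of it. Research Setting and study population gives a different count for the same year: "In 2023 there was a total of 150 of adult cardiac patients admitted post cardiac surgery with a mediastinal incision". The inclusion criterion is "Patients 14 years of age and older scheduled for cardiac surgery requiring a sternotomy incision".

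**What is compared.** Objectives sets the silver dressing against the standard foam dressing on SSI rate, and Data analysis plans a chi-square comparison of the two groups.

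**Local rates.** The abstract's Conclusion says "The current rate of surgical site infection amongst cardiac surgical patients is 2.1 below the benchmark of 2.9". The table under Current cardiac SSI rates lists 5.8 and 5.97 for CABG (2023, 2022) and 1.2 and 1.5 for all cardiac procedures. The text above the table says that the institution did not beat its benchmark.

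**The concern.** Both totals are current text. No dropout allowance, screening figure or distinction between enrolled and evaluable patients connects them. Stopping at 109 or at 150 would each comply with one section, so the planned size could be settled after results are known. Allocation by strict alternation makes each patient's arm known in advance, which gives more reason to fix the stopping point beforehand.

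The stated basis for 109 also does not fit the question. The number of patients admitted in a year says how many can be recruited. It may enter a formula for estimating one proportion in a finite population. It does not determine how well two infection rates can be compared, and using it as the justification hides how little information either total provides.

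**Working it through.** **1. The two totals.** 75 + 75 = 150 and 55 + 54 = 109, so each sum is right. The difference is 150 − 109 = 41, and 150 is 38% larger than 109.

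**2. Share of one year's admissions, before exclusions.** 109/150 = 73% and 109/200 = 55%; 150/150 = 100% and 150/200 = 75%.

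**3. Can 109 be reproduced?** The protocol shows no inputs, so I tried the usual single-proportion formula with finite-population correction (my assumption): n0 = 1.96² p(1 − p)/d², n = n0/(1 + (n0 − 1)/N).

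- N = 150, p = 0.5, d = 5%: n0 = 384, n = 108.1. The variant N/(1 + N × 0.05²) gives 109.1.
- N = 200, p = 0.5, d = 5%: n = 131.8. The variant gives 133.3.
- N = 200, d = 3%: n = 107.9 at p = 5.8% (2023 CABG rate) and 109.3 at p = 5.97% (2022 CABG rate).

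Values of 108 to 109 arise from either admission count under different margins, so the origin of 109 cannot be established. I do not claim that it fails to follow from 200.

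**4. What each total delivers for the SSI comparison.** The powers below come from exact binomial enumeration with 55/54 and 75/75 patients, taking p ≤ 0.05, two-sided (assumed). The protocol states no target difference, so the scenarios are illustrative. Chi-square is the planned test. Fisher is shown because event counts are small.

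| Control v silver | Source of rates | Chi-square, 109 / 150 | Fisher, 109 / 150 | Expected infections in whole trial, 109 / 150 |
|---|---|---|---|---|
| 5.8% v 2.9% | local CABG rate to its benchmark | 11% / 13% | 5% / 5% | 4.7 / 6.5 |
| 10% v 5% | abstract's background rate, halved by me | 18% / 22% | 12% / 13% | 8.2 / 11.3 |
| 19.3% v 9.2% | cited general-surgery study | 33% / 43% | 29% / 34% | 15.5 / 21.4 |

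Expected infections per arm at 5.8% with no effect: 55 × 0.058 = 3.2 and 75 × 0.058 = 4.4.

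The 95% half-width on the risk difference is 1.96 × √[p(1 − p)(1/n1 + 1/n2)]. At p = 0.058 in both arms:

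- 109 patients: 1.96 × √[0.0546 × (1/55 + 1/54)] = 8.8 points.
- 150 patients: 1.96 × √[0.0546 × (2/75)] = 7.5 points.

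The normal approximation is rough with so few events. Newcombe intervals near that rate agree in size: 3/55 v 3/54 gives −10.3 to +10.0 points, and 4/75 v 4/75 gives −8.3 to +8.3. A fall from 5.8% to 2.9%, which is 2.9 points, lies well inside each of these.

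**5. The two admission counts.** The 150 is described as adult patients; the 200 carries no age label, and inclusion starts at 14. They may be different populations, but the text does not say so.

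**6. The rate of 2.1.** For 2023, 2.1% of 327 is 6.9 infections and 2.1% of 69 is 1.4, against 4 listed in each row. Pooling 2022 and 2023 gives 12/203 = 5.9% for CABG and 15/1061 = 1.4% for all cardiac. Read as 2.1 points below 2.9, the rate would be 0.8, which also appears nowhere. In the table, 2.1 occurs only as the operational goal.

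**The case against.** The strongest reply is that the 150 stands in a short abstract and may be stale. Sampling technique is the methods text, carries the recruitment rule and names a calculation whose inputs may sit in an unseen SAP. That is plausible but not shown. An SAP might explain 109, but it would not remove the conflict inside this protocol. It is also no finding here that alpha, power or a target difference is absent from the protocol.

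Several narrower points stand as limits:

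- Power is low at both totals, so the power figures do not measure the 41-patient discrepancy. They show what is at stake whichever total is kept.
- The figure of 3 to 4 infections per arm uses the CABG rate, while eligibility covers any cardiac surgery by sternotomy. The all-cardiac rates of 1.2% and 1.5% would give fewer, about 0.6 to 1.1 per arm.
- The visible text sets no accrual period, so the shares of one year's admissions describe scale and do not prove that recruitment is infeasible.
- The 150 and 200 admissions may both be right, so labels are all that is needed.
- The rate of 2.1 could refer to another period or category. It enters no sample-size statement and is a secondary point.
- The CABG, all-cardiac and 10% literature rates are labelled separately and do not conflict with one another.

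**Conclusion.** The concern holds. The protocol fixes its sample size twice, at 150 and at 109, and its recruitment rule depends on that figure, so the stopping point is contradictory by 41 patients. This rests on the text alone and needs no assumption. It must be put right, because the trial cannot be run or reported to plan while two sizes stand.

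It also holds that an admission count by itself does not size the comparison of SSI rates. How 109 was obtained remains undetermined. On the illustrative rates above, with a two-sided 5% level assumed, chi-square power runs from 11% to 33% at 109 patients and from 13% to 43% at 150. Under either total, a non-significant result could not be read as no effect. The mismatch over the rate of 2.1 is real but carries less weight.

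**What to change.** 1. State one total and one size per arm, identically in the abstract and in Sampling technique. The documents do not show which total is intended; the investigators must say.
2. Label the 150 and 200 admission counts by age range, procedures and period.
3. Present the admission count as a feasibility limit only. Beside the chosen size, state what it delivers: the assumed control rate with its procedure category, the expected number of infections, and the confidence-interval half-width on the risk difference.
4. Reconcile the abstract's rate of 2.1 with the table of local rates, naming category and period. The documents do not show which figure is right.

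The cost is wording only. No extra patients are needed if 109 is confirmed, and up to 41 more than Sampling technique states if 150 is. The downside is that the stated precision will look less favourable.

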## Objectives

1. Assess the effectiveness of the silver dressing on SSIs rates as compared to the standard dressing- Mepilex foam dressing in reducing SSIs.

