## **Principal Investigator:**

**Name (print      Signature: \_\_\_\_\_ Date: \_\_\_\_\_**

## Current cardiac SSI rates at KFSHRC-J

SSIs currently are a challenge amongst cardiac surgical patients. The operational benchmarking for SSIs is 2.9 with an operational goal of 2.1. and with the current numbers of SSIs the organisation was not able to outperform the benchmark. The below graph depicts the rates of SSI for the years 2022-2023.

Category	Benchmark	Operational Goal	Year to Date (2023)			Year to Date (2022)		
			No. of Procedures	No. of Infections	Rate	No. of Procedures	No. of Infections	Rate
CABG	2.9	2.1	69	4	5.8	134	8	5.97
All cardiac		2.1	327	4	1.2	734	11	1.5

Despite defined interventions to reduce SSIs such as the **Bundle of Care Interventions for the Prevention of Healthcare associated infections- CIPP 8834 - SSI Prevention Bundle**, the SSI rates for CABG and cardiac have soared in the latter part of 2023.

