## **Data analysis**

Data analysis will be done using SAS software. Descriptive statistics will include frequencies and percentages. Comparisons between the 2 groups will include chi-square statistic for categorical variables and the t test for continuous variables. Logistic regression will be used to compare the risk of infection according to type of dressing and adjusting for patients' characteristics.

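### The total of 109 is presented as calculated, but the only input named is a yearly patient count, which cannot size a comparison of silver with Mepilex; at the hospital's own SSI rates, power is low even for complete prevention

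*Protocol*

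**What the plan says.** The Sampling technique section of the Protocol opens its sample size text with a yearly count: "In the year 2023 there were a total of 200 patients admitted for a cardiac surgical procedure requiring a mediastinal incision". It continues "Based on this population and sample size calculation- a total of 109 patients will be included" and gives the split: "Ie 55 in the intervention group and 54 in the control group". It states no control SSI rate, target difference, significance level, power or formula.

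The objective is comparative: "Assess the effectiveness of the silver dressing on SSIs rates as compared to the standard dressing". Data analysis plans the matching test: "Comparisons between the 2 groups will include chi-square statistic for categorical variables", with a logistic regression of infection on dressing type.

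Three other places bear on the size:
- Research Setting and study population gives a different count for the same year: "In 2023 there was a total of 150 of adult cardiac patients admitted post cardiac surgery with a mediastinal incision".
- The abstract's Methodology paragraph plans 75 patients per group, 150 in all.
- The section on current cardiac SSI rates, just before the sample size text, tabulates the site's infections. CABG: 4 of 69 in 2023 (5.8%) and 8 of 134 in 2022 (5.97%). All cardiac: 4 of 327 (1.2%) and 11 of 734 (1.5%). The sample size text does not use them.

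**The concern.** The number of patients in the source population matters when the aim is to describe that population with a given margin of error. It has no part in the power of a test between two allocated arms, which depends on the control risk, the difference sought and the arm sizes. The protocol had local control risks at hand and did not use them.

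A reader, or the ethics board, will take the sentence to mean that 109 patients were worked out to answer the silver versus Mepilex question. Nothing shown supports that. At the site's own rates the likely outcome is p≥0.05, and the hospital, which says that it is already introducing silver dressings as standard practice, could take that as evidence of no benefit.

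**Working it through.** **1. Can 109 be reproduced?** The protocol names no formula. The usual one-sample survey formulas were tried with assumed defaults (proportion 50%, margin ±5 points, 95% confidence).

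- Simple form, N/(1 + N × 0.05²). N = 150: 150/1.375 = 109.1. N = 200: 200/1.5 = 133.3.
- Cochran with finite-population correction, 384.16/(1 + 383.16/N). N = 150: 108.1, rounded up to 109. N = 200: 131.75, rounded up to 132.

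So 109 follows from the 150 in the setting section, not from the 200 that the sample size text names. From 200 it is reached only with less usual one-sample inputs (19.3%, ±5 points, 95%: 109.2; 10%, ±5 points, 99%: 109.1). Two-proportion formulas applied to rates in the document did not give 109. The nearest total was 116 (10% versus 0%, one-sided, 80% power).

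**2. What 55 versus 54 delivers.** Assumptions: two-sided 5%, uncorrected Pearson chi-square, no dropout. Power is the sum, over all pairs (a, b) with p≤0.05, of Bin(a; 55, p_silver) × Bin(b; 54, p_control).

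If silver prevents every SSI, then a = 0. Against 0/55, 3/54 gives p = 0.076 and 4/54 gives p = 0.040. Power is therefore the probability of at least 4 infections among 54 controls. Fisher's test needs 5 (4/54: p = 0.057; 5/54: p = 0.027).

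| Control SSI risk | Expected control SSIs (54 × risk) | Complete prevention: Pearson (Fisher) | Halving: Pearson |
|---|---|---|---|
| 1.2% (all cardiac, 2023) | 0.65 | 0.4% (under 0.1%) | 0.3% |
| 1.5% (all cardiac, 2022) | 0.81 | 0.9% (0.1%) | 0.6% |
| 5.8% (CABG, 2023) | 3.13 | 38% (20%) | 11% |
| 5.97% (CABG, 2022) | 3.22 | 40% (22%) | 12% |
| 10% (Background, literature) | 5.40 | 80% (64%) | 18% |

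For the general-surgery study cited in the introduction (19.3% versus 9.2%), power is about 33% (Fisher 29%).

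**3. Does the abstract's 75 + 75 change this?** Complete prevention then has 1.3-2.7% power at 1.2-1.5%, 64-66% at 5.8-5.97% (Fisher 27-29%) and 95% at 10% (Fisher 77%). Halving has 13% at the CABG rates and 22% at 10%.

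**4. Precision.** With no effect of silver, 109 patients would yield 109 × 0.012 = 1.3 SSIs at the lowest local rate and 109 × 0.0597 = 6.5 at the highest. The Newcombe interval combines the Wilson limits (l, u) of each arm: lower = d − √[(p₁−l₁)² + (u₂−p₂)²], upper = d + √[(u₁−p₁)² + (p₂−l₂)²].

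For 1/55 versus 1/54 the Wilson limits are 0.32-9.61% and 0.33-9.77%, and d = −0.03 points. The interval is −8.1 to +7.9 points. For 1/55 versus 2/54 it is −10.8 to +6.4. The half-width of 8 to 9 points exceeds the whole local SSI risk (1.2-5.97%).

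**The case against.** **The size is not hopeless under every rate in the document.** A reader might infer that this trial could not show a benefit even if silver prevented every SSI. The documents do not support that without a condition. The Background puts SSI prevalence in cardiac surgery at about 10%, and there complete prevention has 80% power by Pearson (64% by Fisher). At the CABG rates, 40% is poor but not zero. This objection stands, and it limits the power statement to the hospital's own rates. It does not rescue the design: complete prevention is the largest effect possible, and halving from 10% has only 18% power.

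**The survey formula is an inference.** A reader might conclude that 109 is a survey sample size. The protocol refers to a calculation without showing it. The match needs assumed defaults and the 150 from another section; the 200 actually named gives 132-133. This also stands: the formula is a possible explanation only, and a calculation not shown may exist. The point does not rest on it, since the only input stated is a population count under any reading.

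**The detail may sit in a SAP.** That would excuse a missing formula. It does not excuse a stated basis of the wrong kind in the protocol itself.

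**Feasibility may be the real reason.** Nothing in the document says so, and the protocol should not be told to say it unless it is true.

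**Conclusion.** The point holds in this form. The protocol gives a yearly patient count as the basis for 109 patients. That count does not determine the power or precision of the silver versus Mepilex comparison, and no calculation shown supports the objective or the test. At the local rates, power for complete prevention runs from 0.4% to 40%. At 10% it is 80%, falling to 18% for halving. Choosing 75 + 75 instead raises these figures but does not supply a valid basis.

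The figures assume a two-sided 5% level, the uncorrected Pearson test and no dropout, none of which the protocol states. Fisher's test would lower the power. The conclusion about the stated basis needs none of these assumptions. Nor is it a finding that more patients must be enrolled: the text can be corrected for whichever total is kept.

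**What to change.** 1. Reconcile 109 (55 + 54) with the abstract's 75 + 75, and the 2023 count of 150 with 200. This comes first, because the figures below can be given for one total only.
2. In Sampling technique, remove the statement that the size is based on the population count and give the true basis for the total. Then state what it delivers at the site's tabulated rates and at 10%: the expected number of SSIs, the expected width of the 95% interval for the risk difference, and the power for complete prevention and for halving.
3. In Data analysis, make the difference in one-month SSI risk, with a score-type 95% confidence interval, the headline result. State that p≥0.05 will not be reported as absence of benefit or as equivalence.

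Calling the trial a pilot or estimation study is optional.

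Cost: amended wording in the abstract, setting, Sampling technique and Data analysis text, and one further output in the analysis. No patients are added. The downside is a less favourable stated claim about what the trial can show.

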### **Inclusion criteria**

- Patients 14 years of age and older scheduled for cardiac surgery requiring a sternotomy incision.

### **Exclusion criteria**

- Presence of a concurrent infection and any systemic antibiotic other than those used for the purpose of perioperative prophylaxis.
- Patients who died without an infection within 30 days following surgery.
- Patients who had undergone another procedure through the same incision(s) within a year after enrollment in this study.
- Patients who are a redo- such as needing debridement or an infection.
- Patients that have an open chest
- Patients on ECHMO
- Patients excessively bleeding
- Patients who require the surgery as an emergency
- Patients with a known allergy to silver dressings

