## **Description of intervention**

Intervention will consist of a replacement of the sterile plain postoperative dressing Mepilex border dressing (versatile five-layer all-in-one bordered foam dressing) with the sterile silver-impregnated dressing on 3 units: the CSICU, CVT. The dressing will be applied upon arrival in the CSICU directly on the incision after closure had been performed with sutures and/or staples and the Mepilex border. Dressings will be changed at seven (days) post-surgery (or sooner if oversaturated), and then changed whenever the dressing becomes saturated. Application of the dressing will be discontinued when the incision had epithelialized. There will be no changes in techniques or patient care, and no other changes of any kind (including surgeons) during the entire study period. Throughout the entire period of hospitalization, patients will be monitored for signs and symptoms of infection as per Center for Disease Control [CDC] guidelines ie is superficial, deep, organ space infection (CDC, 2010). Patients will be followed for signs and symptoms of SSIs up to one **month** following surgical intervention. Surgical site infections will be identified through assessment present in chart reviews, clinic visits, readmission to a hospital, laboratory culture surveillance, and telephone interviews at the one month period.

NB: The control group will have the Mepilex foam dressing. All other processes and care will be the same as the intervention group.

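### Two exclusion criteria act after allocation, and the one-year re-procedure rule can delete the deep and organ-space infections the trial is meant to count

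*Protocol*

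**What the plan says.** Under Sampling technique, allocation happens on arrival from theatre: "first patient transferred from OR to the CSICU will be part of the intervention group, second patient part of the control group", alternating until the sample size is reached. That section gives the size as 109 (55 and 54), made up of patients who satisfy the inclusion and exclusion criteria.

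Three items in Exclusion criteria matter here:

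- "Patients who had undergone another procedure through the same incision(s) within a year after enrollment in this study"
- "Patients who died without an infection within 30 days following surgery"
- "Patients who are a redo- such as needing debridement or an infection"

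Description of intervention sets out the outcome. Infection is classed by CDC criteria as "superficial, deep, organ space infection (CDC, 2010"). The time limit is: "Patients will be followed for signs and symptoms of SSIs up to one" month after surgery. Cases are found from chart review and from "clinic visits, readmission to a hospital, laboratory culture surveillance, and telephone interviews at the one month period".

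The protocol nowhere says that patients who meet the first two items after allocation stay in the analysis.

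**The concern.** An eligibility criterion should be decidable when the patient is allocated. The re-procedure item and the death item both describe later events, so they can only remove patients who already have an arm and a dressing.

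The re-procedure item is the serious one. It covers any reopening of the sternotomy, whatever the reason. The death item at least carries a qualifier about infection; the re-procedure item has none. A deep or organ-space SSI that leads to reopening is an outcome under Description of intervention and a ground for removal under Exclusion criteria.

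Three things are at stake: loss of events in a trial that expects few, an SSI rate that reads too low, and a comparison that is no longer between the groups as allocated. If the dressing affects how often infections come to reopening, the removals will differ between arms and the relative risk will be biased.

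**Working it through.** **Timing.** The protocol gives no figure for this point, so the check starts by setting its statements side by side.

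| Item | When it becomes known | Overlap with the endpoint |
|---|---|---|
| Allocation | Transfer from OR to CSICU | – |
| Re-procedure through the same incision | Up to one year after enrolment | Yes: deep or organ-space SSI that is reopened |
| Death without infection | Up to 30 days after surgery | Inclusion depends on the outcome, but no SSI is removed |
| Redo, debridement or infection | Not stated; reads naturally as a baseline redo | Only if applied after allocation |

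Planned SSI follow-up is one month and the re-procedure window is one year. On the planned data, the rule would act on re-procedures seen in the same month in which SSIs are counted.

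**Inputs from the protocol.** N = 109 (Sampling technique). Control SSI risk p0 = 1.2% (all cardiac, 2023) or 5.8% (CABG, 2023), both from the table of current SSI rates, or 10% (Abstract and Background).

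**Assumptions.** The share d of SSIs reopened within the month is 20–50%. Where the dressing works, its relative risk (RR) is 0.3. The protocol gives neither figure.

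**1. Events lost if the dressing has no effect:** N × p0 × d.

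- 1.2%: 109 × 0.012 = 1.3 expected; 0.3–0.7 lost.
- 5.8%: 109 × 0.058 = 6.3 expected; 1.3–3.2 lost.
- 10%: 109 × 0.10 = 10.9 expected; 2.2–5.5 lost.

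The Abstract gives 75 per arm instead. With 150 patients at 5.8%, 150 × 0.058 = 8.7 are expected and 1.7–4.4 lost, the same proportions.

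**2. Control risk as it would read:** (1 − d)p0 / (1 − d·p0). At p0 = 5.8%:

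- d = 0.20: 0.0464 / 0.9884 = 4.7%.
- d = 0.50: 0.0290 / 0.9710 = 3.0%.

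**3. Relative risk at p0 = 5.8%.** Let RRr be the effect on SSIs that are reopened and RRn the effect on the rest. The true RR is d·RRr + (1 − d)·RRn. The observed RR is RRn × (1 − d·p0) / (1 − d·p0·RRr).

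| Effect of dressing | True RR (d = 0.20, 0.50) | Observed RR |
|---|---|---|
| Only on reopened SSIs (RRr 0.3, RRn 1) | 0.86, 0.65 | 0.99, 0.98 |
| Only on the others (RRr 1, RRn 0.3) | 0.44, 0.65 | 0.30, 0.30 |
| Equal on both (0.3, 0.3) | 0.30, 0.30 | 0.298, 0.294 |

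**4. A second set-up.** Take 10% control risk and remove 25% of SSIs in one arm and 50% in the other. Each arm's risk reads p(1 − f)/(1 − p·f), where p is its true risk and f the share of its SSIs removed.

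- No true effect: the two arms read 0.0769 and 0.0526, an RR of 1.46 or 0.68 depending on which arm loses more.
- True RR 0.50: it reads 0.72 if control loses more and 0.33 if silver loses more.
- Equal removal of 25% or 50% leaves a true RR of 0.50 at 0.49.

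**5. Death item.** Take a true RR of 1.00 and an assumed 30-day mortality without infection of 5% in one arm and 1% in the other. The observed RR is 0.99/0.95 = 1.04 or 0.95/0.99 = 0.96.

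**The case against.** The strongest reply is that *after* enrolment is a slip for *before*. The verb tense and a one-year window in a one-month study both point that way, and most of the list describes perioperative status. If so, the main point goes away. But the text says after, and the death item above it shows that the list does contain post-allocation rules. A slip would also need correcting.

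The size of the bias is also open to challenge. It rests on assumed reopening shares and on all-or-none effects by type of infection. That is fair: the protocol neither supports nor excludes unequal removal, and under equal removal the RR hardly changes. At the all-cardiac rate, fewer than one event is lost.

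Step 2 is a special case because it removes only infected patients. Non-infected reopenings leave the denominator too, so the rate reads low only if SSI patients are reopened more often than the rest. With d = 20% and an assumed 5% of non-SSI patients reopened, 5.8% reads 0.0464/(0.0464 + 0.95 × 0.942) = 4.9% instead of 4.7%. This is a small refinement.

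A later chart review could in principle cover the full year. The protocol plans none, and it would remove still more allocated patients.

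Finally, analysis sets are often left to an SAP, which is not at hand. This is not a silence, however: the protocol actively excludes these patients, and an SAP that kept them would contradict it.

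**Conclusion.** The concern holds and must be fixed. That two exclusions act after allocation, and that the re-procedure item can remove outcome events, follows from the text without any assumption.

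The size does depend on assumptions. If 20–50% of SSIs are reopened within the month, that share of the events is lost. In a trial expecting roughly 1 to 11 SSIs in total, this is from under one event to about five. The direction of any bias in the RR cannot be known from the protocol, and the RR figures above are illustrations, not predictions.

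The death item is wrong in principle but minor in effect. The redo item needs only its timing stated.

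**What to change.** - Delete the one-year re-procedure item and the 30-day death item as exclusions. If the sponsor meant a procedure before enrolment, the item must say so and be judged at baseline.
- Keep all other exclusions, including known silver allergy and emergency surgery, and state that they are assessed at or before allocation. State that the redo/debridement/infection item refers to status before allocation.
- Analyse every allocated patient in the assigned arm.
- Count any SSI within the one-month follow-up as an event, including one that leads to reopening or debridement. This also covers an SSI that follows a reopening for another reason.
- Keep patients who die without SSI in the denominator and report deaths by arm.

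The cost is protocol wording only, because the one-month follow-up is already planned. The drawback is that a few early deaths count as non-events; a sensitivity analysis of SSI or death is optional.
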